To evaluate the development of symptomatic COVID-19 or asymptomatic infection in household contacts of study participants after participant receipt of study drug	
Participants with symptomatic COVID-19 among household contactsParticipants with asymptomatic SARS-CoV-2 infection among household contacts
To evaluate the effect of ADG20 on the following parameters 
COVID-19-related mortalityTime to improvement of COVID-19 symptomsPost-acute sequelae of SARS-CoV-2 infection	
COVID-19-related death through Day 29Time to improvement of COVID-19 symptoms through Day 29Incidence of PASC at Day 60, Day 90, and Month 6

ADA=antidrug antibody; AUC =area under the plasma concentration–time curve; AUC_{0-inf}: AUC extrapolated to infinite time; AUC_{0-last}=AUC from zero up to the last concentration \geq lower limit of quantification; CBC=complete blood count; CL=clearance; C_{max}=maximum plasma concentration; IM=intramuscular; NP=nasopharyngeal; PASC=post-acute sequelae of SARS-CoV-2 infection; PK=pharmacokinetic; RT-(q)PCR=(quantitative) reverse transcription-polymerase chain reaction; TEAEs=treatment-emergent adverse events; t_{1/2}=plasma concentration half-life; T_{max}=time to reach C_{max}; Vd=apparent volume of distribution.

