3.4.3. PK and ADA Assessments

On Day 1, a blood sample for PK assessment will be collected prior to study drug administration. Blood samples for PK assessment will also be collected on Days 7, 29, 90, and at Month 6 and Month 11. Blood samples for determination of ADA (and neutralizing antibody) against ADG20 will be collected on Days 1, 29, and 90, and at Months 6 and 11.

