4.5.8. PK Analysis Set

The PK Analysis Set includes all participants in the Safety Set who had at least one measurable ADG20 concentration post-administration of study drug. Where participants experience issues that may affect exposure to study drug (eg, dosing errors, etc), data will be reviewed by the study pharmacokineticist and evaluated for exclusion from the PK analysis set on a case-by-case basis. All participants excluded from the PK analysis set will be documented in the data listings.

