6.3. Serum Pharmacokinetic Parameters

Serum concentration-time data will be analyzed by non-compartmental analysis using Phoenix® WinNonlin® Version 8.0 or higher (Certara USA, Inc., Princeton, NJ). The PK parameters to be calculated for ADG20, where data permit, as listed in [Table 8](#).

Table 8: Calculated PK Parameters

Parameter	Definition
C_{\max}	Maximum observed concentration.
T_{\max}	Time of maximum observed concentration.
$AUC_{0-\text{last}}$	AUC from time 0 to the last measurable observed concentration (C_t), calculated using the linear trapezoidal rule.
$AUC_{0-\infty}$	AUC from time 0 extrapolated to infinity, calculated as $[AUC_{0-\text{last}} + (C_t / \lambda_z)]$.
$T_{1/2}$	Apparent terminal elimination half-life, calculated as: $\ln(2) / \lambda_z$.
CL/F	Apparent total body clearance, calculated as: Dose / $AUC_{0-\infty}$.
V_d/F	Apparent volume of distribution during the terminal phase (for IM dose), calculated as: Dose / $[\lambda_z \times AUC_{0-\infty}]$.

In addition to the PK parameters shown in [Table 8](#), which will be listed and summarized, the parameters in [Table 9](#) will also be listed to document the selection of data points used to estimate $T_{1/2}$ using non-compartmental procedures.

Table 9: PK Parameters for Data Selection

Parameter	Definition
λ_z	Apparent terminal elimination rate constant, where λ_z is the magnitude of the slope of the linear regression of the log concentration versus time profile during the terminal phase.
Number points	Number of data points used to estimate λ_z ; a minimum of 3 data points must be used, and C_{\max} must not be included.
λ_z lower	Lower bound used for the estimation of λ_z .
λ_z upper	Upper bound used for the estimation of λ_z .
Rsq (R2)	R2, the coefficient of determination (goodness of fit statistic); λ_z and all associated parameters will only be reported where $R2 \geq 0.80$.
%AUC _{ext}	Percentage of $AUC_{0-\infty}$ due to extrapolation; $AUC_{0-\infty}$, CL/F and V_d/F values will be flagged and excluded from summary statistics where $%AUC_{ext} > 20\%$.

Actual sampling times will be used for the estimation of all serum PK parameters, and all concentrations will be included in the analysis (including concentrations collected outside predefined collection windows).

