Serum PK parameters will be presented in data listings and summarized separately using descriptive statistics (number of observations, arithmetic mean, SD, CV, geometric mean, geometric CV, median, minimum, and maximum) by part, treatment. T_{\max} will be summarized using number of observations, median, minimum, and maximum only.

In addition, serum PK parameters will be presented in data listings and summarized by ADA status (treatment emergent ADA positive/negative).

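### AUC0-last is summarised with no common end time or completeness rule, so it mixes ADG20 exposure with how many PK visits each participant attended, overall and by ADA status

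*SAP*

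**What the plan says.** SAP Section 2 lists AUC0-last among the secondary PK endpoints, and its footnote gives "AUC from zero up to the last concentration" at or above the quantification limit. The operative rule is SAP Section 6.3, Table 8: "AUC from time 0 to the last measurable observed concentration", by the linear trapezoidal rule.

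After the predose sample, SAP Section 3.4.3 states: "Blood samples for PK assessment will also be collected on Days 7, 29, 90, and at Month 6 and Month 11". SAP Section 4.5.8 admits to the PK Analysis Set any treated participant who "had at least one measurable ADG20 concentration post-administration of study drug". Section 4.1 leaves missing concentrations missing.

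Section 6.3 then summarises the parameters with arithmetic and geometric means, SD, CVs, median and range. It adds that "serum PK parameters will be presented in data listings and summarized by ADA status", meaning treatment-emergent ADA positive or negative. Under Section 5.7.2, treatment-emergent ADA can be found only at Day 29, Day 90, Month 6 or Month 11.

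Table 9 has three quality rules. The three-point minimum and the R-squared threshold govern the terminal slope and the parameters derived from it. The 20% extrapolation limit governs AUC0-inf, CL/F and Vd/F. None of them names AUC0-last.

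**The concern.** For a drug that is cleared within the sampling period, the last measurable concentration is set by the assay, and AUC0-last is close to total exposure for everyone. ADG20 is different. At a half-life of about 97 days, roughly 10% of the peak is still expected at Month 11, so the end of the integral is usually set by the last visit at which blood was drawn. Participants followed for different lengths of time then contribute areas over different periods to the same mean and CV.

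The summary by ADA status is exposed twice. Each further attended visit lengthens the area and also gives another chance to detect ADA. Without any true effect, ADA-positive participants would tend to show the larger AUC0-last, which is the opposite of the direction in which ADA would be expected to act.

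The SAP already applies a completeness rule to a different area: viral load AUC (Section 5.5.4, Table 4) is not calculated if Day 1 or Day 29 is missing, or if more than three values are missing. The PK area has no equivalent.

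**Working it through.** The documents give no figure for AUC0-last, PK attendance, between-participant PK variability or the PK assay limit, so there is no planned figure to reproduce. The check is a model calculation.

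**Inputs**
- Half-life 97 days (protocol 1.1.2.1), so ke = ln 2 / 97 = 0.00715 per day.
- Absorption rate ka = 0.25 per day (assumption). It gives a Day 1 to Day 13 concentration ratio of about 0.25, matching the MN50 titers in protocol 1.3.2.1: 346/1382 = 0.25.
- Nominal sampling at 0, 6, 28, 89, 179 and 329 days after dosing (SAP 3.4.3 and Appendix B).
- One compartment, first-order absorption, linear trapezoid as in SAP Table 8.

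**Concentrations.** C(t) = ka/(ka − ke) × (e^(−ke·t) − e^(−ka·t)), in units of dose/volume: 0, 0.757, 0.842, 0.545, 0.287, 0.098. Month 11 is 329/97 = 3.4 half-lives after dosing.

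**Area to the last sample, same participant**

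| Last sample | Cumulative area | Share of Month 11 value | Range* |
|---|---|---|---|
| Day 7 | 2.27 | 2% | 1–3% |
| Day 29 | 19.85 | 15% | 9–22% |
| Day 90 | 62.15 | 48% | 38–58% |
| Month 6 | 99.56 | 78% | 69–84% |
| Month 11 | 128.41 | 100% | |

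*Half-life 70–150 days, ka 0.1–0.7 per day.

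**Extrapolated share,** (C_last/ke)/(AUC0-last + C_last/ke):
- Month 6: 40.1/(99.56 + 40.1) = 29%.
- Month 11: 13.7/(128.41 + 13.7) = 10%.

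At 97 days, a participant last sampled at Month 6 would therefore typically lose AUC0-inf under the 20% rule while the shortened AUC0-last stays in the summary.

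**Effect on the summary.** Assumed attendance: 80% reach Month 11, and 10%, 5%, 4% and 1% stop at Month 6, Day 90, Day 29 and Day 7.
- Arithmetic mean: 0.80×1 + 0.10×0.775 + 0.05×0.484 + 0.04×0.155 + 0.01×0.018 = 0.908, about 9% low.
- Mean log: 0.10×(−0.254) + 0.05×(−0.726) + 0.04×(−1.867) + 0.01×(−4.036) = −0.177. The geometric mean is e^(−0.177) = 0.838, about 16% low.
- Log variance: 0.0065 + 0.0263 + 0.1394 + 0.1629 − 0.177² = 0.304. Geometric CV = √(e^0.304 − 1) = 60%; the arithmetic CV is about 24%. The Day 7 and Day 29 terms supply (0.1394 + 0.1629)/0.335 = 90% of the log second moment.

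Simulations with other assumed mixes (10%, 20% and 30% incomplete, clearance CV 25%) put the arithmetic mean 5%, 10% and 15% low and the geometric mean 10%, 20% and 28% low. The geometric CV was 0.53, 0.78 and 0.97, against 0.18 with full follow-up.

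**ADA split with no true effect.** Assume a 2% chance of a positive at each attended ADA visit, unrelated to PK. The probability of a positive is 0, 0.020, 0.040, 0.059 and 0.078 for a last visit at Day 7, Day 29, Day 90, Month 6 and Month 11. Under the 80% mix, the mean log share is −0.063 in positives and −0.185 in negatives, so the geometric ratio is e^0.123 = 1.13. Dropping those seen only at Day 7, who have no post-dose ADA sample, makes the negatives −0.144 and the ratio e^0.081 = 1.08. Across the attendance and detection assumptions tried, it ran from about 1.05 to 1.3.

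**The case against.** The strongest reply has four parts.

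1. **Size rests on assumption.** No attendance rate is given, and the design works against early loss. All five post-dose PK visits may be done at home (protocol Table 12-1), missed PK samples may be rescheduled (protocol 6.6), and those withdrawing between Day 29 and Month 6 are encouraged to complete the Month 6 assessments (protocol 4.2.2). This stands. With complete attendance the effect is nil.

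2. **The larger figures are geometric.** Section 6.3 also reports arithmetic mean and median. The arithmetic mean moves 9% in the 80% case, and the median hardly moves when 80% reach Month 11. This stands too: the 60% geometric CV comes mostly from the 5% assumed to stop at Day 7 or Day 29.

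3. **ADA effects can be seen elsewhere.** Section 6.2 summarises and plots concentrations by ADA status, and AUC0-inf, CL/F and Vd/F are covered by the 20% rule. A reader might infer that a real ADA-driven fall in exposure would be hidden. The documents do not support that, because these other measures do not accumulate over visits. Only the AUC0-last row is tilted.

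4. **Unseen material.** The PK assay limit, the PK table shells and the PK Analysis Plan named for the Phase 2 review are not available, parameters are calculated only where data permit, and additional PK parameters are allowed. This limits certainty. But the SAP leaves that condition undefined, and the case-by-case review it does specify concerns dosing problems: "Where participants experience issues that may affect exposure to study drug (eg, dosing errors, etc), data will be reviewed by the study pharmacokineticist". Missed visits are not mentioned.

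**Conclusion.** The point holds as a minor one. As planned, AUC0-last combines ADG20 exposure with length of PK follow-up, and no rule in the SAP separates the two. The per-participant shares (about 2%, 15%, 48% and 78% of the Month 11 value) follow from the half-life and the visit schedule, and they keep their pattern over a wide range of PK assumptions. The effect on the summary depends on attendance, which the documents do not give: none with full attendance, and about 9% (arithmetic) or 16% (geometric) low in the assumed 80% case. The ADA tilt also depends on an assumed detection rate. That the visit rather than the assay sets the last point is likely at this half-life, but cannot be confirmed without the assay limit.

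A reader might go further and say that AUC0-last measures attendance instead of exposure. That is too strong: most of the mean is still exposure in every scenario tried. Nor does the plan contain an age-group comparison of AUC0-last that would be distorted. The table is descriptive, no test or decision depends on it, and efficacy and safety conclusions are untouched.

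**What to change.** In SAP Section 6.3 and Table 8:

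- Add AUC over fixed intervals, for example dosing to Day 29, to Day 90 and to Month 6, in participants whose samples span the interval. Report the number contributing.
- Use the same interval in both groups for the summary by ADA status.
- Summarise AUC0-last only in participants with a Month 11 sample, or list it with the day of the last sample.

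This needs SAP wording and partial-area settings in the PK software, and no new samples. The costs are real but modest. Fewer participants contribute to later intervals, and requiring spanning samples is itself a selection on attendance, so the counts matter. The Day 29 interval rests on two post-dose samples. The Month 6 window is ±30 days, so the SAP must say how a participant sampled early in that window, with no later sample, is handled.

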3. INVESTIGATIONAL PLAN

3.1. Overall Study Design and Plan

ADG20-TRMT-001 is a randomized, double-blind, placebo-controlled, multi-center adaptive study of the mAb ADG20 in the treatment of ambulatory participants with mild or moderate COVID-19. The study will evaluate the safety, efficacy, PK, and antiviral activity of ADG20 300 mg IM versus placebo. A total of approximately 1084 participants are planned to be enrolled in the study at approximately 100 to 115 sites globally.

Participants with laboratory confirmed mild or moderate COVID-19 with symptom duration of 5 days or less prior to randomization and a positive SARS-CoV-2 test taken within 5 days or less prior to randomization will be enrolled. Participants will be randomized 1:1 to receive a single dose of ADG20 or placebo by IM injection. Randomization will be stratified by age (age 12 to 17, 18 to 65, and >65 years) and country.

Study drug will be administered at the study site. As a precaution for acute worsening of disease, hypersensitivity, and/or ISRs, participants will be observed after study drug administration, as described in the protocol (Section 6.4.1). Each participant will receive a single dose of study drug or placebo at the Day 1 Visit. After Day 1, participants will be followed via telemedicine visits, phone calls, or in-person visits, as indicated in the Schedule of Events ([Appendix M](#)), through Month 14/EOS.

3.2. iDMC, Interim, and Final Analyses

An iDMC will provide safety oversight for all parts of the study. The iDMC will meet at designated timepoints, and on an ad hoc basis, to review available safety data, and other clinical study data, to ensure the benefit/risk remains favorable (refer to [Appendix L](#) and below for

details). Details regarding iDMC membership, conduct, ongoing safety monitoring, decision-making, and communication will be provided in the iDMC Charter. PPD is not responsible for producing iDMC reports and will complete analyses after the database locks (Day 29 and Month 14) as detailed below. Pausing guidelines triggering iDMC ad hoc reviews are described in Section 5.8.1.9.

To evaluate the safety profile of ADG20 and to make recommendations regarding enrollment of adolescents and pregnant and breastfeeding women in Phase 3 and postdose monitoring duration, an administrative IA will be reviewed by the iDMC after approximately 200 participants are enrolled in Phase 2.

Following completion of enrollment and completion of the Day 29 visit for all participants (or if it is known that a participant will not have a Day 29 visit), the database will be frozen (soft-locked) to conduct the primary Day 29 analysis. All decisions regarding the analysis will be made in a blinded fashion and the SAP will be finalized (signed) prior to unblinding. The study will be unblinded to Sponsor personnel not working directly with the site staff after this freeze, and an unblinded data analysis will be performed. All site staff, certain Sponsor personnel (or designee) working directly with the site staff, and participants, will remain blinded to individual participant study drug assignment.

The database will be locked for the final safety analysis after all participants have been followed through the Month 14 visit (or if it is known that the Month 14 visit will not occur).

Plans for additional database locks or analyses may be revised during the study to adapt to unexpected issues in study execution, and/or data that affect planned analyses, and/or to address regulatory authority request(s), and/or to address protocol amendments.

3.3. Study Duration

The study duration for each participant will be approximately 14 months. Each participant, regardless of study phase, will receive a single dose of ADG20 or placebo at the Day 1 visit. Participants will have telemedicine visits (via video or phone) and in-person clinic or at-home visits through Day 29. Participants will continue long-term follow-up through Month 14, with additional visits for safety laboratory tests at Day 90 and at Month 6.

3.4. Study Assessments

The Schedule of Assessments is provided in [Appendix M](#). Efficacy and safety assessments will be conducted by site staff, and by participants with at home assessments and collections.

3.4.1. Clinical Efficacy Assessments

Participants will be asked to complete the COVID-19 Symptom Diary (includes global impression questions) daily from Day 1 to Day 29. The investigator (or designee) will assign an overall COVID-19 severity grade for each visit through Day 29. At scheduled visits on Days 3, 5, 7, 11, 14, 21, 29, 60, 90, and at Months 6, 11, and 14, participants (or guardians/LARs) will be asked to report any medically attended visits. Medically attended visits include telemedicine visits not specified in the protocol, emergency room or urgent care center visits, hospitalization, or visits to a physician's office. COVID-19-related medically attended visits include visits for

attention to worsening signs or symptoms attributed to COVID-19 in the opinion of the investigator. The participant's survival status (known to be dead or alive) should be determined at the planned time for any missed visit through Month 14, or at the time that the participant is thought to be lost to follow-up. At Day 29, participants will be asked about household transmission of SARS-CoV-2 and symptomatic COVID-19.

During the long-term follow-up period (LTFU), participants will be asked questions about their overall health status, including return to usual health and usual activities and any ongoing symptoms associated with COVID-19.

3.4.2. Virologic Efficacy Assessments

Blood will be collected on Day 1 to test for SARS-CoV-2 antibodies. Two NP swabs will be collected on Day 1 for SARS-CoV-2 RT-qPCR, SARS-CoV-2 sequencing, and a respiratory panel assessment. One NP swab will be collected on Day 7 for SARS-CoV-2 RT-qPCR and SARS-CoV-2 sequencing. Saliva samples for SARS-CoV-2 RT-qPCR will be collected at the site on Days 1, 7, and 29, and by participants at home on Days 3, 5, 11, 14, and 21.

3.4.3. PK and ADA Assessments

On Day 1, a blood sample for PK assessment will be collected prior to study drug administration. Blood samples for PK assessment will also be collected on Days 7, 29, 90, and at Month 6 and Month 11. Blood samples for determination of ADA (and neutralizing antibody) against ADG20 will be collected on Days 1, 29, and 90, and at Months 6 and 11.

3.4.4. Safety Assessments

Safety will be assessed in an ongoing manner. Blood samples for safety laboratory assessments (hematology, serum chemistry, and coagulation) will be collected on Days 1, 7, 29, and 90, and at Month 6. A complete physical examination will be conducted at screening, and a targeted, symptom-directed review of changes in health based on reported AEs or ongoing signs/symptoms of COVID-19 will be conducted at Days 7, 29, and 90, and at Month 6 and Month 11. Vitals signs (including temperature, heart rate, respiratory rate, seated blood pressure, and SpO₂) will be assessed by site staff after study drug dosing and on Days 7, 29, and 90, and at Month 6 and Month 11 (see [Appendix M](#)). Measurements of temperature, SpO₂, and heart rate are to be taken by the participant daily through Day 29.

AEs occurring from when the participant signs the ICF until the Month 14 visit, or withdrawal from the study, will be recorded. Only study procedure-related AEs occurring before randomization will be recorded. Other AEs, including SAEs and MAAEs, will be collected through Month 14. AESIs (as defined in Section [5.8.1.4](#)) will be recorded through Day 4. Participants will record ISRs using the Injection Site Reaction Diary starting after dosing on Day 1 through Day 4. Investigators (or designee) will follow all ISRs that are ongoing beyond Day 4 to resolution. Hypersensitivity reactions and ISRs that occur after Day 4 will be recorded as AEs.

3.5. Study Endpoints

Study endpoints and corresponding objectives are shown in Section 2. Definitions of the key clinical and virologic endpoints are provided below. Safety endpoints are defined in Section 5.8.

3.5.1. Clinical Efficacy Endpoints

COVID-19-related hospitalization or all-cause death through Day 29 (primary endpoint):

COVID-19-related hospitalizations include visits for attention to worsening signs or symptoms attributed to COVID-19, in the opinion of the investigator.

- **Hospitalization** is defined as ≥ 24 hours of acute care in a hospital or acute care facility (includes emergency rooms, intensive care units, acute care facilities created for COVID-19 pandemic hospitalization needs, or other acute care facilities).
- **Through Day 29** is defined as the admission date for the hospitalization or acute care facility occurring from Day 1 (postdose) up to and including Day 29.
- **All-cause death** is defined as death for any reason from Day 1 (postdose) through Day 29.

Severe/critical COVID-19 or all-cause death through Day 29: All-cause death is defined as death for any reason from Day 1 (postdose) through Day 29. Severity is based on the investigator's assessment of severity (eCRF COVID-19 Severity Assessment) per the following protocol definitions:

- **Severe COVID-19** is defined as having a positive test by standard RT-PCR assay or equivalent test plus the following:
 - Symptoms suggestive of severe systemic illness with COVID-19, which could include any symptom of moderate illness or shortness of breath at rest, or respiratory distress including the need for initiation of oxygen therapy.
 - Clinical signs suggestive of severe systemic illness with COVID-19, such as respiratory rate ≥ 30 breaths per minute, heart rate ≥ 125 beats per minute, $\text{SpO}_2 \leq 93\%$ on room air at sea level or ratio of arterial oxygen partial pressure to fractional inspired oxygen ($\text{PaO}_2/\text{FiO}_2$) < 300 mm Hg.
 - No criteria for critical severity.
- **Critical COVID-19** is defined as having a positive test by standard RT-PCR assay or equivalent test plus evidence of critical illness, defined by at least one of the following:
 - Respiratory failure based on resource utilization requiring at least one of the following:
 - Endotracheal intubation and mechanical ventilation, oxygen delivered by high-flow nasal cannula (heated, humidified, oxygen delivered via reinforced nasal cannula at flow rates > 20 L/min with fraction of delivered oxygen ≥ 0.5), noninvasive positive pressure ventilation, extracorporeal membrane oxygenation, or clinical diagnosis of respiratory failure (ie, clinical need for one of the preceding therapies, but the preceding therapies cannot be administered in setting of resource limitations).

- Shock (defined by systolic blood pressure <90 mmHg, diastolic blood pressure <60 mmHg, or requiring vasopressors). **Note:** Shock is per investigator diagnosis/assessment.
- Multiorgan dysfunction/failure.

Note: A clinical diagnosis of respiratory failure (in the setting of resource limitation) in which the management deviates from standard of care should be recorded as part of formal data collection.

Regardless of investigator's assessment of severity, severe/critical COVID-19 will be imputed for participants who met the primary efficacy endpoint definition in the analysis.

COVID-19-related emergency room visits, COVID-19-related hospitalization, or all-cause death through Day 29: Defined as any stay in a hospital or acute care facility regardless of duration (includes emergency rooms, intensive care units, acute care facilities created for COVID-19 pandemic hospitalization needs, or other acute care facilities) for attention to worsening signs or symptoms attributed to COVID-19 in the opinion of the investigator or all-cause death through Day 29.

COVID-19-related medically attended visits or all-cause death through Day 29: Defined as for the primary efficacy endpoint, but also includes any medically attended visits, in-person, or telemedicine, not specified in the protocol. These include unscheduled in-person or telemedicine visits conducted by the investigator for the purpose of evaluating worsening signs or symptoms attributed to COVID-19 or emergency room, urgent care center or physician office visits, or hospitalization for attention to worsening signs or symptoms attributed to COVID-19, in the opinion of the investigator.

Time to sustained recovery (improvement or resolution) of COVID-19 symptoms through Day 29: Defined as the time from the first dose date to the earliest date when sustained improvement or sustained resolution of COVID-19 symptoms is met (as detailed below) through Day 29. COVID-19 symptoms assessed include fever, chills, cough, sore throat, congestion, shortness of breath/difficulty breathing at rest, shortness of breath/difficulty breathing with exertion, muscle or body aches, fatigue, headache, nausea, vomiting, and diarrhea. Loss of taste/smell is excluded from this analysis.

Time to sustained improvement of COVID-19 symptoms through Day 29: Defined as the time from the first dose date to the first date when all of the above symptoms are scored as moderate or severe at baseline are scored as mild or absent, all of the above symptoms scored as mild or absent at baseline are scored as absent, and with no symptom worsening or new symptoms, except for cough, fatigue, and headache which may be mild or absent, through Day 29.

Time to sustained resolution of COVID-19 symptoms through Day 29: Defined as time from the first dose date to the first date when all of the above symptoms are scored as absent with no symptom recurrence or new symptoms, except cough, fatigue, and headache which may be mild or absent, through Day 29.

Censoring rules for time to COVID-19 symptoms through Day 29 analysis:

- Participants who are randomized but not treated are censored at Day 1.

- Participants who have any COVID-19-related hospitalization (≥ 24 hours) or all-cause death through Day 29 (as defined in the primary endpoint) will be censored at Day 30.
- Participants who have not been followed through Day 29 visit (discontinuation from study or incomplete follow-up at the time of analysis) will be censored at the last contact date.
- Participants who have completed the Day 29 visit and do not experience a defined event through Day 29 will be censored at Day 30.

[Table 2](#) provides further programming details.

Table 2: Criteria for Sustained Improvement and Sustained Resolution of COVID-19 Symptoms Through Day 29

COVID-19 Symptoms	Baseline Severity	Criteria for Sustained Improvement	Criteria for Sustained Resolution
Fever, chills, sore throat, congestion, shortness of breath/difficulty breathing at rest, shortness of breath/difficulty breathing with exertion, muscle or body aches, nausea, vomiting, diarrhea	Moderate/Severe	Mild/Absent with no worsening (moderate/severe)	Absent
	Mild	Absent	with no recurrence or new symptoms (mild/moderate/severe)
	Absent	with no recurrence or new symptoms (mild/moderate/severe)	
Cough, fatigue, headache	Moderate/Severe	Mild/Absent	Mild/Absent
	Mild	with no worsening (moderate/severe)	with no worsening (moderate/severe)
	Absent		

All-cause mortality through Day 29, Day 60, and Day 90: Defined as death for any reason from Day 1 (postdose) to Day 29, Day 60, and Day 90. In the overall survival analysis, participants who are alive or lost to follow-up at the time of analysis will be censored at the date of last contact.

COVID-19-related mortality through Day 29: Defined as death directly due to COVID-19 or any death for which COVID-19 or COVID-19 complications contributed to the death, as determined by the investigator, a formal autopsy report or death certificate, as recorded on the Death eCRF.

